#### 9.4 Analysis Plan

Each of the primary and secondary outcome measures will be analyzed for the intent-to-treat population and for the evaluable participant population. Major differences in the results, if any, will be further explored. While there is every intention to be complete in describing the analyses to be performed, it is not possible to anticipate every contingency and some adjustments may be required to meet constraints posed by the structure of the data.

Equality of groups at baseline will be established by comparing demographic and drug use information collected on the ASI. A test of proportions will be used for main outcomes evaluated at treatment end. Continuous on-study data will be evaluated using three-factor analysis of covariance with detoxification schedule as one factor (fixed effect), stabilization dose as the second factor (fixed effect), and site as the third factor. Baseline demographic values, where they potentially affect the responses on study or where they are found to be unevenly distributed between groups at baseline despite randomization, may be investigated post hoc. Interaction effects including, but not necessarily limited to, taper schedule X dose, will be investigated post hoc. Repeated measures, survival, and time course analyses will be employed where appropriate.

Statistical tests will be two-sided at a 5% level of alpha. Confidence intervals will be two-sided with a 95% confidence coefficient.

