## 3.0 Study Design

This is a randomized, parallel-group, open-label study. After screening and baseline assessments, participants will receive a three-day Suboxone induction and a 25 day stabilization, (total 28 day stabilization phase). For three weeks (days -28 to -8) the dosing is flexible, but in the final week of the stabilization phase (days -7 to -1 and randomization day 0), participants must be on a stable dose of either 8mg, 16mg, or 24mg of buprenorphine. On day 0 participants will be randomly assigned in a 1:1 ratio to one of two Suboxone tapering regimens. If, for some reason, the participant is unable to attend on day 0, there will be a 3 day window for randomization to occur. Regardless of the actual day on which randomization occurs, it will be named as day 0 (it may occur up to, but no longer than, three days after the actual day 0). Randomization will be stratified, within site, according to the dose being taken on day 0 (8, 16 or 24 mg of buprenorphine). Tapering regimen #1 will be performed over 7 days and regimen #2 will be performed over 28 days. Participants in both groups will be seen weekly for data collection through day 56, followed by a 3 month post randomization visit on Day 84 for both groups and a 3 month post taper follow-up on days 91 and 112 respectively. This design will allow the investigators to analyze the data in either a post taper or a post randomization design. All participants will participate in an equal number of data collection visits throughout the study. Data will be available for 1 and 3 Months Post Taper, as well as 1 and 3 Months Post Randomization.

The maximum length of study participation is expected to be approximately 5 months, including screening, stabilization, tapering, post-tapering and follow-up. All participants will also participate in TAU from the time of consent through at least the end of the taper, at the CTP that manages their study participation. Following the taper, participants may continue in TAU at the CTP or be referred to other available local resources.

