#### 4.5 Randomization

Participants completing the pre randomization period (-28 to -1) will be randomly assigned, on day 0, to one of two taper schedules. If for some reason, the participant is unable to attend on day 0, there will be a 3 day window following day 0 for randomization to occur. All participants must be randomized by the third day, or they will be dropped from participation. Participants who do not complete the stabilization period, or who are not randomized, may be replaced in order to obtain the appropriate randomized sample size per site. Regardless of the actual day on which participants are randomized, the day of randomization becomes day 0. The first day of either taper schedule begins on Day 1. On Randomization Day 0, participants will be given the medication for the taper, explicit written instructions detailing exactly how to take the medication for the next seven days, and told to begin the taper with the first dose on the following day (Day 1).

Protocol # CTN-0003

Page 18 of 44

Version 7C

Although participant assignment to group will be performed at the site (CTP), the randomization cards will be prepared in advance by the Data Management Group of the Pacific Region Node (Lead Node). We expect some variation in the number of participants stabilized on each of the three doses, and we will provide sites with an adequate supply of randomization envelopes for each dose. Each CTP will receive three sets of randomization cards: one set for participants on the 24 mg dose, one set for participants on the 16 mg dose, and one set for participants on the 8 mg dose. Research assistants will be instructed simply to pull the next consecutive card from the pile corresponding to the participant's dose at the time of randomization. Participants will be assigned to the tapering schedule using a 1:1 ratio of random assignment; that is, regardless of the stabilization dose, each participant will have an equal chance of being assigned to the 7 day or the 28 day taper schedule. Participants will participate in treatment as usual at each site (CTP) during screening, stabilization, tapering and follow-up, or may be referred, following taper, to other appropriate treatment services.

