#### **9.2 Outcome Measures**

#### Primary Outcome Measure

In keeping with this hypothesis, there is one primary outcome, the proportion of participants providing opiate free urines in each group on the day following the end of the taper. This outcome will be evaluated at the end of the taper. It will also be evaluated at 1 and 3 months post completion of tapering.

Secondary Outcome Measure

Several secondary outcomes will be evaluated. These include:

- 1. Comparison of number of opiate free participants by stabilization dose and taper schedule.
- 2. Comparison of:
  - a. The number of opiate free urine specimens at follow-up
  - b. The number of all drug free urine specimens at follow-up
  - c. Frequency of concomitant medication used to treat withdrawal symptoms
  - d. Severity of withdrawal symptoms as assessed by COWS and ARSW
  - e. The mean VAS craving level of each group
  - f. The mean SQ score (participant satisfaction) of each group
  - g. The number and severity of adverse event

These measures will be analyzed within a time course framework. We will compute change from baseline to follow-up in measures taken only at those timepoints (ASI). For measures collected repeatedly throughout the taper schedule (COWS, ARSW, SQ, concomitant meds, adverse events), we will plot the pattern of responses by group over time.

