## 9.6 Sample Size Estimate

The sample size determination was based on how many opiate users seeking treatment that the sites are capable of recruiting. With 11 sites, each site would be responsible for randomizing approximately 44 participants. It is possible that recruitment may not be

Protocol # CTN-0003

Version 7C

Date of Preparation: 1/31/05

Page 37 of 44

adequate at some sites and therefore enrollment may not be equal across sites. The total N will remain at 480

In a Phase III study for evaluation of the efficacy and safety of the combination product of buprenorphine and naloxone in opiate dependence, Study 1008, the percent of participants with opiate free urine samples after four weeks of treatment was 5.8% in the placebo group, 21% in the buprenorphine group and 18% in the combination group. Assuming that the percent of opiate free urine samples in a control group is 20%, the difference of 12% is considered a clinically significant improvement, and 240 participants per group would provide approximately 82% power for detecting this 12% difference. If 20% of participants dropout in the current study, and dropout occurs at random, then the sample size of 240 participants per group will provide 72% power for detecting a difference of 12%.

In Study 1008A, the mean craving score at Week 4 was 55.1 in the placebo group, 29.8 in the monotherapy group and 33.0 in the combination group. The standard deviation of VAS was estimated from the confidence interval for the difference between treatment groups presented in the 1008 study report. It was estimated to be 40.7. The sample size of 240 per group will provide at least 90% power to detect a difference between the mean craving scores of 33 and 44 at the 0.05 level.

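### The primary binary outcome is assigned a test of proportions with no adjustment for the randomization strata, a valid choice that may give up a few points of power

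*Protocol*

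**What the plan says.** Section 9.2 states that "there is one primary outcome, the proportion of participants providing opiate free urines in each group on the day following the end of the taper". For this outcome Section 9.4 gives one method: "A test of proportions will be used for main outcomes evaluated at treatment end". Tests are two-sided at 5%.

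The design is stratified. Section 3.0 says "Randomization will be stratified, within site, according to the dose being taken on day 0 (8, 16 or 24 mg of buprenorphine"). Section 4.5 puts this into practice with three sets of cards at each site, from which staff "pull the next consecutive card from the pile corresponding to the participant's dose at the time of randomization". Allocation is 1:1. No blocking or block size is stated.

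For continuous outcomes Section 9.4 does use the design factors, through a "three-factor analysis of covariance with detoxification schedule as one factor (fixed effect), stabilization dose as the second factor (fixed effect), and site as the third". Adjustment for demographic covariates at baseline, and interactions, are left to post hoc work (Sections 9.4, 9.5 and 9.7).

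Opiate-free status by dose and schedule appears in Section 9.2 as a secondary comparison. A urine drug screen is scheduled for all participants on Day 0 (Table 1) and is taken before medication is dispensed (Section 7.25).

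**The concern.** The factors that govern randomization enter the analysis of the continuous outcomes but not, as written, that of the single primary outcome. When assignment is balanced within strata that predict the outcome, the treatment comparison is less variable than an unstratified test assumes. The test then rejects less often than 5% under the null, its interval is somewhat too wide, and power is lost.

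The protocol has little power to spare. Section 9.6 takes the sample size from what the sites can recruit and states 72% power after 20% dropout. The same text also leaves unused a baseline measurement of the same kind as the endpoint.

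**Working it through.** **1. Which test the protocol's power figures imply.** Inputs from Section 9.6: control rate 20%, difference 12 points (so 32%), 240 per group, or 192 per group after 20% dropout (240 × 0.8). From Section 9.4: two-sided 5%. The mean rate is 0.26.

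Power = Φ[(0.12 − c − 1.96·SE0)/SE1], with SE0 = √(2·0.26·0.74/n), SE1 = √((0.20·0.80 + 0.32·0.68)/n), and c = 1/n with the continuity correction or 0 without.

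- n = 240: SE0 = 0.0400, SE1 = 0.0397. Corrected: (0.12 − 0.0042 − 0.0785)/0.0397 = 0.94, power 82.7%. Uncorrected: 85.2%.
- n = 192: SE0 = 0.0448, SE1 = 0.0443. Corrected: (0.12 − 0.0052 − 0.0877)/0.0443 = 0.61, power 72.9%. Uncorrected: 76.6%.

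The stated figures of about 82% and 72% therefore match an unstratified, continuity-corrected two-proportion test. This supports reading the named test as unstratified.

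**2. Effect of ignoring the strata.** Eleven sites by three doses give 33 strata, averaging 480/33 ≈ 15 participants. The following were assumed, because the protocol gives none of them: the spread of control rates across strata, a dose mix of 15/35/50%, and permuted blocks of 4. Marginal rates were held at 20% and 32%. There were 40,000 simulated trials per setting, without continuity correction. Each cell shows the unstratified test, then Cochran-Mantel-Haenszel (CMH) over the 33 strata.

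| Control rates across strata | Type I error, N = 480 | Power, N = 480 | Power, N = 384 (20% dropout) |
|---|---|---|---|
| 20% everywhere | 0.051 / 0.050 | 85.6 / 85.3% | 76.9 / 76.5% |
| 11–35% (mild) | 0.048 / 0.050 | 85.4 / 85.7% | 76.8 / 77.0% |
| 7–46% (moderate) | 0.047 / 0.051 | 86.1 / 87.0% | 77.5 / 78.7% |
| 3–63% (strong) | 0.038 / 0.049 | 86.9 / 89.2% | 77.8 / 81.1% |
| 2–76% (very strong) | 0.032 / 0.049 | 87.6 / 91.5% | 79.0 / 84.3% |

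If cards within a stratum are not blocked, the unstratified test stays at 0.050 in the three settings tried (mild, moderate and strong). The 33-stratum CMH then has less power than the unstratified test under mild heterogeneity (83.9 vs 85.7%) and moderate heterogeneity (84.2 vs 85.0%). It gains only under strong heterogeneity (87.2 vs 85.3%).

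**3. Adjusted logistic regression, with and without Day 0 urine.** Dropout of 20% at random, blocks of 4, 3,000 trials per setting (simulation error about 0.7 points). Site SD and dose step are on the log-odds scale. Half of participants are assumed to have a favourable Day 0 result.

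| Assumed prognostic strength | Unadjusted | Logistic | Gain (points) |
|---|---|---|---|
| Site 0.5, dose 0.4 | 77.0% | 78.9% | 1.9 |
| Site 0.8, dose 0.6 | 78.4% | 82.0% | 3.6 |
| Site 0.5, dose 0.4, Day 0 urine OR 2.7 | 77.8% | 81.0% | 3.2 |
| Site 0.5, dose 0.4, Day 0 urine OR 4.5 | 77.2% | 83.2% | 6.0 |
| No site or dose effect, Day 0 urine OR 4.5 | 77.1% | 80.6% | 3.5 |

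The adjusted type I error was 4.8 to 5.6% in these settings, so a small part of the gain may reflect a test slightly above nominal. In the last row the gain comes entirely from the baseline urine and does not need prognostic strata.

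**The case against.** The strongest reply is that nothing here is an error of validity. Randomization makes the crude comparison unbiased, the type I error is not inflated, and the loss is small under most plausible settings. All of that stands.

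A reader might go further and infer that the strata are known to be prognostic and that the test is therefore conservative. The protocol does not support this. It nowhere says that site or dose predicts opiate-free urine. It hypothesizes a benefit regardless of dose and makes the role of dose a secondary question. Conservatism also needs balance forced by blocking, and Section 4.5 mentions none.

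Nor can the 72% be blamed on the ignored strata. It is what the unstratified formula gives at 192 per group, and about 4 points of the shortfall come from the continuity correction (76.6% against 72.9%).

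The odds ratio for Day 0 urine is likewise assumed, and leaving out an optional covariate is not a mistake.

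Finally, a test of proportions does not strictly exclude a stratified version, and a statistical analysis plan that is not shown may specify one. That limits the point but does not remove it. The protocol does name a method, its power figures match the unstratified form, and it treats the continuous outcomes differently. Listing dose as a secondary comparison does not change the primary test.

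**Conclusion.** The point holds as a missed improvement. The primary analysis as written is valid and unbiased but does not use the factors on which participants are randomized.

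If assignment is blocked and the strata are prognostic, the test is mildly conservative. The power lost is about 0 to 2 points under mild to moderate heterogeneity and about 2 to 5 under strong heterogeneity. With no heterogeneity, or without blocking, its type I error is at the nominal level. Adjusting for the Day 0 opiate urine as well would give a total gain of about 3 to 6 points if its odds ratio is about 2.7 to 4.5.

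These sizes rest on assumed heterogeneity, block size, dose mix and covariate strength. The inconsistency between the design and the primary test rests on the text alone. Because the remedy needs no new data, it should be made before outcome data are seen.

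**What to change.** Replace the sentence in Section 9.4 with wording such as: The primary outcome will be compared by logistic regression with taper schedule, stabilization dose (three levels), site and Day 0 opiate urine result as main effects, and reported as a standardized risk difference with a 95% CI by the delta method or bootstrap. Crude proportions by group will be given as description. A Cochran-Mantel-Haenszel test stratified by dose and site will be supportive, with small strata pooled by a rule set in advance.

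Main effects are preferable to 33 separate strata in the primary model. At a site that randomizes 25 participants (the lower end in Section 3.1), a stratum averages about 25/3 ≈ 8. The standardized risk difference keeps the result on the scale of the 12-point difference used for planning. Section 4.5 should also say whether the cards are blocked; the block size can stay in a restricted document.

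The cost is slightly more analysis work and one pooling rule. All the variables are already collected.

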## 7.21 Addiction Severity Index Lite (ASI-Lite)

The ASI Lite is a standardized, multidimensional, semi-structured, comprehensive clinical interview, which provides clinical information important for formulating treatment plans as well as problem severity profiles in six domains commonly affected in substance abusers (McLellan et al., 1985). The domains covered are chemical abuse (alcohol and drug), medical, psychiatric, legal, family/social and employment/support. Composite scores for each problem domain are derived mathematically and used as change measures or outcome indicators as a function of treatment intervention. This instrument also provides clinically necessary information on whether the participant is at imminent risk for suicide, thus permitting evaluators to implement any needed immediate and/or early intervention strategies. A revised version of the ASI Fifth Edition, 1997 version (ASI Lite), that includes only those questions used to derive the composite scores along with some demographic information will be administered by a research staff member having at least a Bachelor's degree in the social sciences or equivalent training and experience as determined by the site's investigator. Composite scores will be calculated according to the procedures described by McGahan et al. (1982), Carroll et al. (1994). The ASI Lite will be administered at screening and at each of the 1 and 3 month Post Taper Follow-Up visits for each group.

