## 9.5 Descriptive Statistics

Summaries of the characteristics of the participant population in both treatment arms at baseline will be prepared to investigate group equality at baseline as well as provide information necessary for decisions about covariates in post hoc analyses. A summary will be prepared to show dropouts/retention over time in each treatment group. The number of missing observations will be compared between treatments. The compliance of each group at each assessment day will be summarized.

Treatment effects will be summarized by gender, ethnicity, and age group separately. No attempt will be made to assess these factors together in order to maintain power for the main comparisons.

All adverse events will be reported in tabular form indicating the frequency of each type of event by various demographic characteristics such as gender, ethnicity, age, duration of addiction, other medical problems both related to and independent of the addiction.

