## 9.7 Post Hoc Analyses

During the course of conducting the primary and secondary analyses, the data may suggest other interesting differences in the treatment groups. Post hoc analyses are anticipated to explore these findings. One potential post hoc analysis would be the exploration of factors found to be significantly different between groups at baseline, as they relate to study outcomes. Another potential post hoc analysis would be the exploration of interaction effects in the Analysis of Covariance (ANCOVA) models of continuous data, including but not necessarily limited to, taper schedule X dose interactions. Still another possible post hoc analysis would be to look at the group differences based on intent-to-treat samples using randomization as the starting point of treatment. Analyses would then be conducted on data from 1 Month Post Randomization and at 3 Months Post Randomization (rather than post taper as in the primary analysis). This is made possible by the design, because participants in both groups are seen for equal contacts following randomization.

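### Section 9.4 names an analysis of covariance but lists no covariate; adding the Day 0 COWS, ARSW and VAS scores would gain precision at no cost

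*Protocol*

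**What the plan says.** **The model.** Protocol section 9.4 gives the analysis of continuous outcomes: "Continuous on-study data will be evaluated using three-factor analysis of covariance with detoxification schedule as one factor (fixed effect", then "stabilization dose as the second factor (fixed effect), and site as the third factor". No continuous baseline term is listed.

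**Baseline variables.** Section 9.4 goes on to a further group of variables: "Baseline demographic values, where they potentially affect the responses on study or where they are found to be unevenly distributed between groups at baseline". It leaves these as something that may be looked into afterwards, without committing to it. There are thus two triggers, possible effect on response and observed imbalance, and both lead only to optional later work on demographics. Section 9.5 says that baseline summaries will "provide information necessary for decisions about covariates in post hoc analyses". Section 9.7 lists as one possible post hoc analysis the "exploration of factors found to be significantly different between groups at baseline, as they relate to study outcomes".

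**What is collected before the taper.** Table 1 marks COWS, ARSW and VAS at Day 0 for all participants, and sections 7.19, 7.20 and 7.22 require them at each clinic visit. Section 4.5 starts both tapers on Day 1. For the ASI the baseline is the screening interview: "The ASI Lite will be administered at screening and at each of the 1 and 3 month Post Taper Follow-Up visits for each group". The Satisfaction Questionnaire (SQ) has no baseline value; Table 1 and section 7.24 place it only at the end of taper and at the 1 and 3 month post-taper visits.

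**Other uses of baseline.** Section 9.2 computes change from baseline for the ASI and plots COWS and ARSW by group over time. Section 9.4 also allows repeated-measures analyses where they are suitable.

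**The concern.** The name of the model and its content disagree: an analysis of covariance with three factors and no covariate is a three-way analysis of variance. The pre-taper score on the same scale is an obvious candidate covariate and is already on the schedule, but the stated model does not use it. Withdrawal and craving are named secondary objectives (section 2.0, items 2d and 2e), so the lost precision falls on outcomes the trial sets out to compare.

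The post hoc rule is also weak. Under randomization, chance alone makes about 1 in 20 baseline variables differ at the 5% level, and such a difference says nothing about whether the variable predicts outcome. A covariate chosen because it happened to differ is chosen after seeing the data. In an open-label trial, a covariate fixed in advance is the safer course.

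**Working it through.** **Inputs.** From section 9.6: SD of VAS craving 40.7, mean scores 33 and 44 (difference 11), 240 per group, 20% dropout (240 × 0.8 = 192 per group). From section 9.4: two-sided 5%. The correlation r between the Day 0 score and the outcome score is not in the Protocol; it is assumed here to lie between 0.2 and 0.6.

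**The plan's own figure.** Section 9.6 states at least 90% power for craving. With power = Φ(δ / (σ√(2/n)) − z):

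- Standard error at 240 per group: 40.7 × √(2/240) = 3.715, and 11 / 3.715 = 2.961.
- Two-sided 5%: Φ(2.961 − 1.960) = 84.2% (noncentral t: 84.0%).
- One-sided 5%: Φ(2.961 − 1.645) = 90.6%.

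The stated figure is therefore reached only with a one-sided test, while section 9.4 fixes two-sided tests. That mismatch is a separate matter. The starting point used here is 84.2%.

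**With 192 per group.** Standard error 40.7 × √(2/192) = 4.154; 11 / 4.154 = 2.648; Φ(2.648 − 1.960) = 75.4%.

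**Adding the Day 0 score.** The covariate reduces the residual SD to 40.7 × √(1 − r²), that is, it removes a fraction r² of the variance. Putting this SD into the same formula, two-sided:

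| Assumed r | Residual SD | Power, 240 per group | Power, 192 per group | n per group for 90% |
|---|---|---|---|---|
| none | 40.70 | 84.2% | 75.4% | 288 |
| 0.2 | 39.88 | 85.6% | 77.1% | 277 |
| 0.3 | 38.83 | 87.4% | 79.3% | 262 |
| 0.4 | 37.30 | 89.8% | 82.4% | 242 |
| 0.5 | 35.25 | 92.8% | 86.4% | 216 |
| 0.6 | 32.56 | 95.9% | 91.2% | 185 |

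Two-sided power of 90% at 240 per group needs a residual SD of 37.17, so r = √(1 − (37.17/40.7)²) = 0.41.

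**Why a covariate and not a simple change score.** With equal SDs before and after, a change score has SD 40.7 × √(2(1 − r)). At r = 0.3 this is 48.16, which gives 70.6% power at 240 per group, worse than ignoring baseline. At r = 0.5 it is 40.7, no gain at all. The covariate form does not carry this penalty.

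**The case against.** **The covariates could stand in a statistical analysis plan that is not shown.** This is fair, and the absence of a covariate list is not by itself the point. But section 9.4 goes beyond silence: it states a model with three named terms and places baseline demographics in post hoc work. A later plan that added the Day 0 score would improve on that model, and the improvement can be made here.

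**A reader might infer that the planned model is chosen by observed imbalance.** The text does not support this. Imbalance is one of two triggers, the other being a possible effect on response. The rule covers demographics in optional analyses already labelled post hoc; the main model stays as schedule, dose and site. What stands is that imbalance is a poor ground for choosing covariates even there.

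**A reader might infer that the Day 0 scores are thrown away.** That is too strong. Section 9.2 plots COWS and ARSW over time, and section 9.4 leaves room for repeated-measures analyses, which could include Day 0. Neither commits to baseline adjustment.

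**A reader might infer that all continuous outcomes lose precision.** SQ has no Day 0 value, so nothing can be gained there.

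**The gain may be small.** Day 0 is scored on a constant dose after stabilization and the outcome after the drug is withdrawn, so a low correlation is plausible. At r = 0.2 the gain at 240 per group is only 1.4 points. Because dose and site are already in the model, the relevant r is the partial correlation given them. Both points stand and limit the size, not the direction.

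**Screening ASI data are a legitimate description of the groups.** This is accepted; no fault is claimed in describing them that way.

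**Conclusion.** The point holds as a free improvement to the analysis of secondary outcomes. Section 9.4 labels the model an analysis of covariance, gives it no covariate, and omits pre-taper scores that the trial already collects.

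For craving, adding the Day 0 score raises two-sided power from 84% to between about 86% (r = 0.2) and 96% (r = 0.6) at 240 per group, and from 75% to between about 77% and 91% at 192 per group. This rests on an assumed r, on the Protocol's SD of 40.7, and on dropout at random in the 192 case. It also takes the Day 0 scales as completed before the participant learns the assignment; the sections cited place them before the first taper dose but do not give the order within Day 0. No similar calculation is possible for COWS and ARSW, for which the Protocol gives no SD.

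It would be wrong to conclude that the trial's result is biased or its main conclusion at risk. Leaving out a baseline score does not bias a randomized comparison, and the primary outcome is binary and compared by a test of proportions. The change should be made, but the trial does not depend on it.

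**What to change.** In section 9.4, replace the model sentence with wording such as:

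> Each continuous outcome with a pre-taper measurement will be analysed by ANCOVA with taper schedule, stabilization dose, site and the baseline value of that measure. The baseline value is the Day 0 score for COWS, ARSW and VAS and the screening value for ASI composite scores. Outcomes with no baseline value (SQ) will be analysed with the three factors only.

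In sections 9.4, 9.5 and 9.7, remove observed baseline imbalance, including statistical significance at baseline, as a reason for choosing covariates. Keep the baseline table as description. Any further covariate should be named in advance because it is expected to predict the outcome.

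This fits the ASI change scores in section 9.2: once the baseline value is in the model, the schedule effect is the same whether the response is the follow-up score or the change.

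The cost is wording only. The measurements are already in Table 1, and no visit, instrument or participant is added. If the order of events on Day 0 is not already fixed in site instructions, one line asking for the scales before the randomization card is drawn would settle it.
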